3.2 Safety Validation

The first portion of the study will preliminarily establish the tolerability of the combination of pembrolizumab, oxaliplatin and capecitabine at the RPTD in patients with metastatic esophagogastric adenocarcinoma. Subjects on this portion of the study will only be enrolled at the Duke Cancer Institute.

A total of five (5) evaluable patients will be accrued and their safety data after completion of the first cycle of safety assessments will be reviewed before additional patients are enrolled. Proceeding to dose expansion cohort will be dependent on DLT (refer to [Section 3.2.1](#)) within the safety validation cohort.

The following enrollment method will be employed for the safety validation stage of the study:

- If no DLT occurs with the 5 evaluable subjects, enrollment may proceed to the dose expansion cohort.
- If 1 DLT occurs with the 5 evaluable subjects, enrollment may proceed to the dose expansion cohort.
- If ≥ 2 DLTs occurs with the 5 evaluable subjects, enrollment must not proceed to the dose expansion cohort and alternative dose levels for oxaliplatin and capecitabine may be considered.

3.2.1 Dose Limiting Toxicity

Using the NCI-CTCAE version 4.0, the following adverse events will be considered dose limiting toxicity (DLT) if occurring during the first cycle (21 days) of treatment and deemed to be related to study treatment:

- Grade 4 neutropenia, thrombocytopenia or anemia.
- Grade ≥ 3 neutropenia or thrombocytopenia lasting over 7 days.
- Grade 3 thrombocytopenia associated with bleeding.
- Neutropenic fever.
- Grade ≥ 3 nausea/vomiting or diarrhea lasting ≥ 3 days despite adequate supportive measures.
- Grade ≥ 3 ALT, AST, or bilirubin elevation > 7 days.
- Grade ≥ 3 non-hematologic toxicity excluding alopecia, anorexia, fatigue, hypertension, isolated lab abnormalities (not clinically significant) and/or allergic or idiosyncratic reactions to any of the study drugs. Anorexia, fatigue and hypertension will be considered as DLT only if they reach Grade 4 or are considered unmanageable.
- Treatment delay of ≥ 14 days for Cycle 2 due to unresolved treatment-related toxicity.

Management and dose modifications associated with all adverse events are outlined in Section 7.0.

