2. To explore other changes in tissue and blood based biomarkers and their correlation with clinical outcomes.
3. To explore changes in immune cells and biomarkers in those who completed treatment and remain in complete response.

Patient Population

Histologically and/or cytologically documented and radiographically measurable (by RECIST 1.1) adenocarcinoma of the esophagus or stomach (HER2 negative) that is metastatic/recurrent and not amenable to potentially curative treatment (e.g., inoperable metastatic or locally recurrent disease). HER2 positive patients would be considered eligible only if there is a contraindication to Herceptin.

Study Design

The study will be conducted in two stages: 1) safety validation and 2) dose expansion.

1. Safety Validation Cohort: The first portion of the study will preliminarily establish the tolerability of the combination of pembrolizumab, oxaliplatin and capecitabine. Five (5) patients will be enrolled and their safety data after 21 days of treatment will be reviewed before additional patients are enrolled. Subjects on this portion of the study will only be enrolled at the Duke Cancer Institute.

2. Dose Expansion Cohort: The second portion of the study (ie. phase II) will enroll 30 patients. In the dose expansion cohort, the first cycle will be modified to allow one week of pembrolizumab monotherapy before starting capecitabine and oxaliplatin (XELOX) chemotherapy, which will allow analysis of biomarkers related to pembrolizumab. Subjects on this portion of the study will be enrolled at the Duke Cancer Institute and select external collaborating institutions.

Number of Subjects

In the Safety Validation Cohort, 5 evaluable subjects will be enrolled.

In the Dose Expansion Cohort, 30 evaluable subjects will be enrolled.

A total of 35 evaluable subjects will be accrued to this study to assess the efficacy, safety and tolerability of the combination of pembrolizumab, oxaliplatin and capecitabine.

Estimated Length of Study Participation

Estimated duration of subject enrollment is 12 months.

Patients will continue to receive study treatment until they experience unacceptable drug-related toxicity or disease progression. The maximum duration of treatment for pembrolizumab will be up to two years. The duration of treatment for XELOX will be until unacceptable drug-related toxicity or disease progression.

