3.0 STUDY DESIGN

3.1 Study Description

This is a single arm, phase II study to assess the safety, tolerability, and efficacy of the recommended phase II dose (RPTD) of the combination of pembrolizumab, oxaliplatin and capecitabine in patients with previously untreated metastatic esophagogastric adenocarcinoma. The study will be conducted in two stages: 1) safety validation and 2) dose expansion. Approximately 50 subjects may be accrued to ensure the trial obtains 5 evaluable subjects in the safety validation cohort and 30 evaluable subjects in the dose expansion cohort. Patients will be enrolled at the Duke Cancer Institute and select external collaborating institutions (dose expansion cohort only).

- Enrolled subjects are defined as subjects who give informed consent.
- Screen failures are defined as subjects who give informed consent and do not meet eligibility criteria.
- Accrued subjects are defined as subjects who give informed consent and meet eligibility criteria.
 - Withdrawal: Subject accrued but later withdrawn from the study, either before or after receiving a study drug.
 - Evaluable: In the Safety Validation Cohort, subjects who are accrued, received study treatment, and completed the first cycle of safety assessments or have dose limiting toxicity (DLT) which is study treatment related that precludes completing the full cycle of assessments will be considered evaluable for DLT. All subjects (in Safety Validation and Dose Expansion) who are accrued and receive any study treatment will be considered evaluable for toxicity. All subjects in Safety Validation and Dose Expansion who are accrued and receive any study treatment will be considered evaluable for efficacy.
 - Non-evaluable: In the Safety Validation Cohort, subjects who accrued but did not complete the first cycle of safety assessments due to reasons other than study treatment-related toxicity (e.g. disease progression or inter-current illness) are considered non-evaluable for DLT.

Table 3.1 Cohorts

Cohort	No. Evaluable Subjects	Oxaliplatin mg/m ² IV, Day 1 every 21 days*	Capecitabine mg/m ² PO, BID Days 1-14 every 21 days*	Pembrolizumab mg IV, Day 1 every 21 days*
Safety Validation	5	130	850 or 1000**	200
Dose Expansion	30	130	850 or 1000**	200

*For dose expansion cohort, Cycle 1, biomarker cycle, is 28 days in length. Cycles 2 and beyond are 21 days.

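### A 14-day Cycle 2 delay is listed as a DLT but cannot be established before about Day 36, while the five-patient gate can be applied at the end of Cycle 1

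*Combined protocol and SAP*

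**What the plan says.** Section 3.2.1 counts the listed events as DLTs "if occurring during the first cycle (21 days) of treatment" and judged treatment-related. The last item on the list is a treatment delay of at least 14 "days for Cycle 2 due to unresolved treatment-related toxicity".

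The review is timed by Cycle 1. For the five run-in patients, the Synopsis (Study Design) says that "their safety data after 21 days of treatment will be reviewed before additional patients are enrolled". Section 3.2 says that "their safety data after completion of the first cycle of safety assessments will be reviewed before additional patients are enrolled". Under section 3.1 a treated patient is evaluable for DLT if they "completed the first cycle of safety assessments or have dose limiting toxicity (DLT) which is study treatment related".

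The gate is in section 3.2. With 0 or 1 DLT in five evaluable patients, expansion is permitted. With two or more, "enrollment must not proceed to the dose expansion cohort and alternative dose levels for oxaliplatin and capecitabine may be considered". Section 3.3 repeats the limit of one DLT, by reference to the definition in section 3.2.1.

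**The concern.** There are two separate problems.

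- **Wording.** Read literally, the 21-day limit excludes the delay item, because a 14-day delay to a cycle due on Day 22 always ends after Day 21. Some other items, such as Grade 3 or higher neutropenia for more than 7 days, may run past Day 21 if they start late, but they can be met inside the window. The delay item never can.
- **Timing.** Suppose the item is read generously, so that the toxicity need only start in Cycle 1. The patient still becomes evaluable, and the review may still take place, when Cycle 1 ends. Nothing makes the review wait for Cycle 2 to start or for the 14 days to pass.

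The gate turns on one DLT versus two and decides whether 30 more patients are treated, some at external sites. A pre-specified DLT rule should lead any two readers to the same count for the same patient at the time of the decision. This one does not.

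**Working it through.** **Day count.** Inputs: a 21-day cycle for the Safety Validation Cohort (Synopsis, Study Drug Regimen) and the 14-day criterion (section 3.2.1). The protocol puts Cycle 2 on Day 29 after the 28-day biomarker cycle, so the convention is cycle length + 1.

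- Cycle 2 due: 21 + 1 = Day 22.
- Delay first established: 22 + 14 = Day 36.
- If the delay ran from the edges of the ±3-day Cycle 2 window (section 5.2): Day 33 to Day 39.
- The review is possible from about Day 22 of the fifth patient, leaving a gap of about 14 days.

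**Events that reach DLT mainly through the delay item.** Most related non-hematologic toxicity of Grade 3 or higher is already a DLT. What remains is mainly persistent Grade 2 toxicity. Under section 7.1.2, clinically significant Grade 2 non-hematologic events hold both chemotherapy drugs until Grade 1 or less. Under section 7.1.1, Grade 2 pneumonitis, colitis or AST/ALT elevation withholds pembrolizumab, with a steroid taper of at least four weeks. That matters here only if a pembrolizumab hold alone is a treatment delay, which the protocol does not say.

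**How many patients could be pending.** Inputs: 35 patients and "Estimated duration of subject enrollment is 12 months" (Synopsis). Assumption: even spacing, including through the single-centre run-in.

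- Spacing: 365 / 35 = 10.4 days.
- On the fifth patient's Day 22, the fourth is at Day 32.4 (3.6 days short of Day 36) and the third at Day 42.9. So at most two are pending.
- Expansion enrolments in the gap: 14 / 10.4 = 1.3.

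**Effect on the gate.** The protocol gives no operating characteristics for the gate, so there is no figure to reproduce. Assumptions, neither in the documents: a true DLT probability *p* of 20% to 40%, of which *s* = 3, 5 or 10 percentage points qualify only through the delay. A pending patient then shows a DLT at review with probability *p* − *s*. Each entry is the chance of 0 or 1 visible DLT in five.

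| *p* | All counted | One pending (*s* = 3 / 5 / 10 points) | Two pending (*s* = 3 / 5 / 10 points) |
|---|---|---|---|
| 20% | 0.737 | 0.750 / 0.758 / 0.778 | 0.762 / 0.778 / 0.818 |
| 30% | 0.528 | 0.541 / 0.549 / 0.569 | 0.553 / 0.570 / 0.612 |
| 40% | 0.337 | 0.347 / 0.354 / 0.372 | 0.358 / 0.372 / 0.408 |

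With one pending, the rise is *s* × P(exactly one DLT in the other four) = *s* × 4*p*(1 − *p*)³.

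- Smallest: 0.03 × 4 × 0.40 × 0.216 = 0.010.
- Largest: 0.10 × 4 × 0.30 × 0.343 = 0.041.

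With two pending, P(open) = A0 × (B0 + B1) + A1 × B0, where A is binomial(3, *p*) and B is binomial(2, *p* − *s*). At *p* = 0.30 and *s* = 0.10 this is 0.343 × (0.64 + 0.32) + 0.441 × 0.64 = 0.6115, a rise of 0.6115 − 0.5282 = 0.083, the largest in the table.

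**First triplet dose in expansion.** Section 3.1 says "Enrolled subjects are defined as subjects who give informed consent", so expansion consent follows the review. Chemotherapy starts on Cycle 1 Day 8 (section 5.2). In the fifth run-in patient's days, the first triplet exposure is 22 + 0 + 7 = Day 29 with no screening time, and 22 + 7 + 7 = Day 36 with one week of screening.

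**The case against.** The best defence is that the 21-day limit applies to adverse events and a delay is not one. The adverse event is the unresolved toxicity, which begins in Cycle 1, and the delay measures how long it lasts. The rival reading makes a listed criterion impossible to meet. This is the sensible reading. A reader might infer from the 21-day limit that the item is void and such patients are never to be counted, but listing the item shows the opposite intent. The defence does not reach the timing of the review, which still follows Cycle 1.

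The gate also does not force an early decision. The review point is an earliest time, expansion at 0 or 1 DLT is permitted and not required, and section 3.3 relies on the full DLT definition. A Cycle 2 on hold would be obvious at the one run-in centre, and section 11.7 has the Lead PI monitoring adverse events throughout. All of this stands as mitigation. But these safeguards rest on discretion; none says how to count a patient who is on hold on the day of the review.

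The set of delay-only events is also narrow. Section 7.1.2 keeps both chemotherapy doses for Grade 2 vomiting and Grade 2 neutropenia, and the oxaliplatin neurotoxicity guidance holds oxaliplatin while the other two drugs may continue. That stands, and it argues for the lower shares in the table.

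A reader might go further and infer that the gate will wrongly send the regimen to 30 patients. The documents do not support that. The bar on proceeding is written on DLTs occurring in the five patients, so it may still apply to a second DLT found on Day 36.

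**Conclusion.** The point holds: as written, expansion can open while a listed DLT in a run-in patient is still undetermined. This is a fault in the safety rule that should be corrected, with a small practical effect. A single late DLT changes the decision only if exactly one other has been counted, and the main consequence is opening up to about two weeks early. With one patient pending, the chance of opening rises by about 1 to 4 percentage points.

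The figure of about 8 points should not be quoted as typical. It needs two patients pending and a 10-point delay-only share, and at the average accrual pace the fourth patient is pending for only about 4 days. These are chances of opening early, not of a lasting wrong decision.

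The day count follows from the protocol. The probabilities rest on assumed DLT rates and delay-only shares, and the limit of two pending rests on even accrual, which the protocol does not guarantee for the run-in.

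**What to change.** In section 3.2.1, state that treatment-related toxicity starting in Cycle 1 that delays Cycle 2 by 14 days or more past its due date (Day 22, so Day 36) counts as a DLT even though the delay is established after Day 21.

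In the Synopsis (Study Design) and sections 3.1 and 3.2, state that if a run-in patient's Cycle 2 is on hold for treatment-related toxicity at the review, that patient is not counted as DLT-free. Expansion then stays closed until the patient:

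- starts Cycle 2;
- meets a DLT criterion;
- reaches Day 36; or
- leaves study treatment or dies for a reason unrelated to study-treatment toxicity.

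The last condition prevents a patient who progresses, withdraws or dies for an unrelated reason from keeping the gate shut. Limiting the hold to toxicity avoids a wait for patients whose Cycle 2 is late for other reasons.

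The cost is protocol wording, plus a wait of up to about two weeks only when a run-in patient's Cycle 2 is on hold for toxicity.

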3.3 Dose Expansion Cohort

Once 5 evaluable subjects have been treated in the safety validation cohort with no more than one occurrence of DLT as defined in Section 3.2.1, the second portion of the study (ie. phase II) will accrue

30 evaluable patients to assess the safety, tolerability, and efficacy of the RPTD of the combination of pembrolizumab, oxaliplatin and capecitabine in patients with previously untreated metastatic esophagogastric adenocarcinoma. Subjects on this portion of the study will be enrolled at the Duke Cancer Institute and select external collaborating institutions.

In the dose expansion cohort, the first cycle will be modified to allow one week of pembrolizumab monotherapy before starting XELOX chemotherapy, which will allow analysis of biomarkers related to pembrolizumab; thus Cycle 1 for the dose expansion cohort will be 4 weeks.

4.0 SUBJECT SELECTION

4.1 Inclusion Criteria

1. Histologically and/or cytologically documented and radiographically measurable (by RECIST 1.1) adenocarcinoma of the esophagus or stomach (HER2 negative only) that is metastatic/recurrent and not amenable to potentially curative treatment (e.g., inoperable metastatic or locally recurrent disease). HER2 positive patients would be considered eligible only if there is a contraindication to Herceptin.
2. No prior chemotherapy for metastatic/recurrent disease. Prior adjuvant or neo-adjuvant treatment with a fluoropyrimidine or fluoropyrimidine based regimen is allowed only if it is completed at least 6 months prior to the start of study drug, whether given alone or with radiation therapy. Patients who have received prior neo-adjuvant therapy (chemotherapy and/or radiation therapy) which did not contain 5-FU or capecitabine and have been diagnosed with metastatic disease (with no previous treatment in the metastatic setting) are eligible. No 6-month window is required for these patients. In the setting of metastatic disease requiring local palliation, only radiosensitizing doses of 5-FU or capecitabine monotherapy are permitted.
3. Prior radiation therapy is permitted, provided it is completed at least 28 days prior to the start of study drug.
4. Age \geq 18 years with ability to understand and willingness to provide informed consent.
5. ECOG performance status of 0 or 1.
6. Adequate organ and marrow function as defined below by the following:
 - a) Absolute neutrophil count (ANC) \geq 1500 μ l
 - b) Platelets \geq 100,000/ μ l
 - c) Hemoglobin (Hgb) \geq 9 g/dL
 - d) Total bilirubin \leq 1.5 x upper limit of normal (ULN)
 - e) AST/ALT \leq 2 x ULN without liver metastasis; \leq 5 x ULN with liver metastasis
 - f) Creatinine clearance \geq 50 cc/min

4.2 Exclusion Criteria

1. Prior therapy with an anti-PD-1, anti PD-L1, anti-PD-L2, anti-CD137 antibody, or anti-cytotoxic T-lymphocyte-associated antigen-4 (CTLA-4) agents.
2. Chemotherapy, targeted small molecule therapy, experimental agents, prior therapy with anti-tumor vaccines or other immune-stimulatory antitumor agents, or biological cancer therapy (including monoclonal antibodies) within 14 days prior to the start of study drug, or not recovered (\leq grade 1 or baseline) from adverse events due to a previously administered agent.

3. Known CNS metastases and/or carcinomatous meningitis. Patients with radiated or resected lesions are permitted, provided the lesions are fully treated and inactive, patients are asymptomatic, and no steroids for treatment of CNS lesion have been administered for at least 30 days prior to the start of study drug.
4. Documented history of clinically significant autoimmune disease (other than well-controlled hypothyroidism) or a syndrome that requires systemic steroids or immunosuppressive agents. Subjects with vitiligo, type I diabetes mellitus, psoriasis not requiring systemic treatment, or conditions not expected to recur in the absence of an external trigger are permitted to enroll.
5. Receiving systemic steroid therapy or any form of immunosuppressive therapy within 1 week prior to the start of study drug. Note: Patients are permitted to receive up to 12 mg dexamethasone prior to administration of oxaliplatin and low dose steroids for up to 48 hours after dosing to prevent nausea and vomiting.
6. Received a live vaccine within 4 weeks prior to the start of study drug.
7. Has known history of, or any evidence of active, non-infectious pneumonitis.
8. Known history of HIV seropositivity, hepatitis C virus, acute or chronic active hepatitis B infection, or other serious chronic infection requiring ongoing treatment. Patients receiving prophylactic antibiotics (e.g., for prevention of urinary tract infection or chronic obstructive pulmonary disease) are eligible.
9. Pregnant or breastfeeding.
10. Not willing to use an effective method of birth control (refer to Section 6.5.1 for acceptable methods of contraception).
11. Concurrent severe and/or uncontrolled medical conditions, which may compromise participation in the study, including impaired heart function or clinically significant heart disease.
12. Current use of medications specified by the protocol as prohibited for administration in combination with study drug. This includes patients with a condition requiring systemic treatment with either corticosteroids (>10 mg daily prednisone equivalents) or other immunosuppressive medications within 14 days prior to the start of study drug (see section 6.5.2 for exception for prophylactic use with oxaliplatin dosing). Inhaled or topical steroids and adrenal replacement doses > 10 mg daily prednisone equivalents are permitted in the absence of active autoimmune disease. Corticosteroids administered as pre-medication for IV contrast allergy are also allowed.
13. Recent or current active infectious disease requiring systemic antibiotics, antifungal, or antiviral treatment within 2 weeks prior to the start of study drug. Subjects being treated for Helicobactor pylori infection are an exception and are allowed to start protocol based therapy while still on antibiotics.
14. Major surgical procedure, open biopsy, or significant traumatic injury within 28 days prior to the start of study drug (56 days for hepatectomy, open thoracotomy, major neurosurgery) or anticipation of need for major surgical procedure during the course of the study (except for the planned metastatectomy).
15. Serious, non-healing wound, ulcer, or bone fracture.
16. History of myocardial infarction, NYHA class III or IV congestive heart failure, unstable angina, cardiac or other vascular stenting, angioplasty, or surgery within 6 months prior to the start of study drug.

17. History of other carcinomas within the last five years, except cured non-melanoma skin cancer, curatively treated in-situ cervical cancer, or localized prostate cancer with a current PSA of <1.0 mg/dL on 2 successive evaluations, at least 3 months apart, with the most recent evaluation no more than 4 weeks prior to the start of study drug.

4.3 Inclusion of Women and Minorities

Men and women of all races and ethnic groups are eligible for this trial.

5.0 STUDY ASSESSMENTS

Note: After Cycle 1, if the subject is unable to have a study assessment taken within the defined time window due to an event outside of his or her control (e.g., clinic closure, personal emergency, inclement weather, vacation), the assessment should be performed as close as possible to the required schedule.

Refer to [Appendix D](#) for Study Calendar.

5.1 Screening Period

During the Screening Period, subjects are consented and screened for the study. Informed consent must be obtained before initiation of any screening procedure that is performed solely for the purpose of determining eligibility for this study. Evaluations performed as part of routine care before informed consent can be considered as screening evaluations if done within the defined screening period, and if permitted by the local Institutional Review Board (IRB)/ Independent Ethics Committee (IEC) policies. Study eligibility is based on meeting all of the inclusion criteria and none of the exclusion criteria (refer to [Section 4.0](#)) before the first dose of study drug on Cycle 1 Day 1.

The following study procedures must be done within 28 days prior to Cycle 1 Day 1:

- Demographics
- Medical and cancer history
- Physical examination
- Height
- Vital signs and weight
- Concomitant medications
- ECOG performance status (perform or repeat within 7 days prior to dosing on Cycle 1 Day 1)
- Thyroid function tests
- Adverse event assessment (review of baseline symptoms)
- Tumor assessment (CT and/or MRI scans)
- Blood tumor marker, if clinically indicated (e.g., CEA or CA19-9)
- Archived tumor tissue (if available)
- PBMC (may be collected pre-dose on Cycle 1 Day 1)
- Plasma (may be collected pre-dose on Cycle 1 Day 1)
- Whole blood (may be collected pre-dose on Cycle 1 Day 1)

The following study procedures must be done within 7 days prior to Cycle 1 Day 1:

- CBC with differential
- Chemistries including liver function tests (LFTs)
- Serum pregnancy test (only for women of childbearing potential)

- Tumor biopsy (only applicable to patients in dose expansion that have lesions amenable to safe biopsy)

Subject eligibility is determined using lab results obtained up to 7 days prior to Cycle 1 Day 1. Any laboratory assessments repeated on Cycle 1 Day 1 must meet eligibility requirements. The Screening Period ends upon receipt of the first dose of study drug or final determination that the subject is ineligible for the study.

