8.2 Circulating Immune Cells (PBMC)

Peripheral blood will be collected for peripheral blood mononuclear cells (PBMCs) from each subject at the following timepoints: baseline, end of monotherapy lead-in on Day 8 (biomarker cycle of dose

expansion cohort only), end of first cycle of combination therapy on Day 29 (biomarker cycle of dose expansion cohort only), first restaging only, disease progression or treatment discontinuation, and for complete responders on long term follow-up. Refer to *Study Manual* for collection and submission details.

PBMCs will be processed and stored by the Duke Immune Profiling Core facility under the direction of [name]. Polychromatic flow cytometry (PFC) panels will be used to compare treatment related changes in both tumor and peripheral immune cell compartments. Up to 50 markers may be analyzed using 3 PFC panels: 1) a 12-color 'Exhaustion Panel', 2) a 12-color 'Tumor Reactive T Cell Panel', and 3) a 14-color regulatory T cell (Treg) and myeloid-derived suppressor cells (MDSC) panel. This analysis will be overseen by [name].

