- Capecitabine (see [Section 6.4](#)) is taken on Days 1-14 of each cycle except for first cycle (ie. biomarker) cycle of dose expansion cohort only when taken on Days 8-22 (ie. pembrolizumab monotherapy lead-in period).
- Radiographic assessments (ie. restaging scans) include CT and/or MRI of chest, abdomen and pelvis after every 3 cycles (9 weeks). Same method for tumor assessment should be employed at every assessment.
- If clinically indicated (ex. CEA and/or CA19-9).
- If FFPE tumor tissue is available, refer to [Section 8.1](#) and Study Manual.

17. For patients accrued to the dose expansion cohort with tumor lesion that is amenable to safe biopsy, pre-treatment (up to 1 week prior to pembrolizumab monotherapy lead-in) and on-treatment (C1 D7 or D8, prior to oxaliplatin and capecitabine/end of one week pembrolizumab monotherapy lead-in in Cycle 1) tumor biopsies will be performed in the first cycle (ie. biomarker cycle). Refer to [Section 8.1](#) and Study Manual.
18. Peripheral blood collection for PBMCs (see [Section 8.2](#) and Study Manual) at the following time points: baseline (may be obtained on Cycle 1 Day 1 prior to the first dose of study drug); end of monotherapy lead-in on Day 8 (biomarker cycle of dose expansion cohort only), end of first cycle of combination therapy on Day 29 (biomarker cycle of dose expansion cohort only), first restaging only (ie. after Cycle 3), and disease progression or treatment discontinuation. Note – There is no PBMC collection at 30-day off treatment follow-up.
19. Peripheral blood collection for plasma (see [Section 8.3](#) and Study Manual) at the following time points: baseline (may be obtained on Cycle 1 Day 1 prior to the first dose of study drug); end of monotherapy lead-in on Day 8 (biomarker cycle of dose expansion cohort only), end of first cycle of combination therapy on Day 29 (biomarker cycle of dose expansion cohort only), each restaging, disease progression or treatment discontinuation and 30-day off treatment follow-up.
20. Peripheral blood collection for whole blood (see [Section 8.4](#) and Study Manual at the following time point: baseline (may be obtained on Cycle 1 Day 1 prior to the first dose of study drug).
21. After every 3 cycles.
22. After the last dose of study drug.

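### Baseline PBMC and plasma may be drawn up to 28 days before dosing, so the Day 8 blood change can include up to 28 untreated days, including recovery from a treated infection

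*Combined protocol and SAP*

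**What the plan says.** **Baseline blood.** Section 5.1 opens its longer screening list with "The following study procedures must be done within 28 days prior to Cycle 1 Day 1". PBMC and plasma are on that list, each with permission, but no requirement, to draw at the dosing visit: "PBMC (may be collected pre-dose on Cycle 1 Day 1" and "Plasma (may be collected pre-dose on Cycle 1 Day 1". Appendix D footnotes 18 and 19 use the same permissive form: "baseline (may be obtained on Cycle 1 Day 1 prior to the first dose of study drug".

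**Follow-up blood.** In the dose expansion cohort the next sample is at the "end of monotherapy lead-in on Day 8" (Section 8.2; Section 8.3 has the same timepoint for plasma). Oxaliplatin and capecitabine start after that draw.

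**Tissue.** Section 5.1 puts the pre-treatment biopsy in the separate 7-day list, and Section 8.1 and Appendix D footnote 17 agree.

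**Washouts, all counted back from study drug.**
- Section 4.2, exclusion 13: "Recent or current active infectious disease requiring systemic antibiotics, antifungal, or antiviral treatment within 2 weeks prior to the start of study drug".
- Section 4.2, exclusion 5: "Receiving systemic steroid therapy or any form of immunosuppressive therapy within 1 week prior to the start of study drug".
- Section 4.2, exclusion 12: more than a stated steroid dose, or "other immunosuppressive medications within 14 days prior to the start of study drug".
- Radiation (Section 4.1, criterion 3) and major surgery (Section 4.2, exclusion 14): 28 days, or 56 days for certain operations.

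**Screening-period prohibitions.** Section 6.5.2 bars systemic glucocorticoids and antineoplastic therapy during Screening as well as Treatment. Contrast premedication is among the steroid exceptions. It has no corresponding rule for infection or anti-infective drugs.

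**Use of the blood data.** Section 8.2 treats the flow cytometry changes as related to treatment. Section 8.3 names CRP and interleukins and correlates analyte changes with PFS and OS. Section 9.1.3 extends the paired pre- versus on-treatment analyses to the Section 8 biomarkers, without multiplicity adjustment.

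**The concern.** The dose expansion cycle was lengthened by a week so that biomarker changes could be attributed to pembrolizumab before chemotherapy starts. That attribution needs a baseline close to the first dose. If the baseline is taken two to four weeks earlier, anything that changes in the interval is counted in the pembrolizumab week. A resolving infection is the plainest case, because CRP and other inflammatory markers can be expected to fall as it clears.

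The trial has one arm and no untreated comparison, and no adjustment for draw date is stated. Drift before dosing therefore cannot be separated from drug effect by the planned analysis. Blood is also the only biomarker-cycle material for patients without a lesion that can safely be biopsied (Section 8.1).

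**Working it through.** **1. The plan's nearest figure.** Section 9.1.3 gives 90% power for a 0.53 SD paired difference with 25 pairs at one-sided alpha 0.1. This is stated for tissue CD8 and PDL1; no figure is given for blood. Noncentrality is 0.53 × √25 = 2.65, with 24 degrees of freedom and a critical t of 1.318. Exact power is 0.907, so the figure reproduces.

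**2. Day arithmetic** (Sections 5.1 and 8.2).

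| Baseline draw | Days from draw to Day 8 | Days on pembrolizumab | Untreated share |
|---|---|---|---|
| Day 1, pre-dose | 7 | 7 | 0% |
| 7 days before (the biopsy limit) | 7 + 7 = 14 | 7 | 7/14 = 50% |
| Day -28 (permitted) | 28 + 7 = 35 | 7 | 28/35 = 80% |

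The last row is the extreme. The on-drug share ranges from 20% to 100% with the draw date, and the documents give no distribution of draw dates.

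**3. Which events fit inside the window.**
- *Infection.* The washout covers the last 14 of the 28 days. The other 28 - 14 = 14 days (Days -28 to -15, half the window) are open to sampling during treated infection in an eligible patient.
- *Radiation and surgery.* Both must precede dosing by at least 28 days, so any in-window draw comes after them. A draw soon after either requires both to lie near Day -28.
- *Steroids and chemotherapy.* Section 6.5.2 closes most of this route. What remains is contrast premedication and carry-over from treatment stopped before Screening.

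**4. Illustration of size.** The documents supply no drift value, so everything in this step is assumed. Let the paired change have SD 1 and no drug effect, and let a fraction f of patients show a 1 SD fall between an early draw and Day 8 for unrelated reasons. The mean change is then -f and its SD is √(1 + f(1 - f)). The standardized drift is d = f / √(1 + f(1 - f)), and the noncentrality is d√n. Take n = 30, the planned cohort size and so the most pairs to expect, with a two-sided paired t-test at alpha 0.1. For f = 0.10, d = 0.10/1.044 = 0.096 and d√30 = 0.525, which gives a rejection rate of about 14%. Simulation agrees with this formula to within about half a percentage point throughout.

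| Patients affected | False-positive rate (nominal 10%) |
|---|---|
| 2% | about 10% |
| 5% | about 11% |
| 10% | about 14% |
| 20% | about 26% |
| 30% | about 43% |

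With 25 pairs, the last three rows become about 13%, 23% and 37%.

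**5. One-sided version.** The plan's t-test power statement uses one-sided alpha 0.1, where direction matters. At 10% affected and 30 pairs, the rate is about 22% when testing for a fall and about 4% when testing for a rise.

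**The case against.** The strongest reply is that this is a narrow problem in hypothesis-generating data.

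- **Scope.** The primary biomarker endpoints are tissue CD8 and PDL1, and the pre-treatment biopsy already has a 7-day window. PFS, response, OS and safety do not use these samples. This stands in full.
- **Steroids.** A reader might infer from the one-week and 14-day exclusions that many baselines could be drawn on steroids. The documents do not support that, because Section 6.5.2 bars systemic glucocorticoids throughout Screening, with exceptions. The same section bars antineoplastic therapy, which largely removes the 14-day prior-therapy washout as a route.
- **Magnitude.** An affected patient must be drawn early, have a resolving event, and shift in the same direction as the others. Nothing in the documents says that 10% or more of patients would meet all three conditions. At 2% to 5% the error rate is close to nominal.
- **Unseen material.** Sections 8.2 and 8.3 refer collection details to a Study Manual that is not supplied and may set a tighter date.
- **Partial mitigation.** Section 6.5.1 requires concomitant medication to be recorded from consent, so treated infections after that point can be identified.
- **Timing.** This is version 9.0, dated March 2022, of a protocol first issued in 2017. Samples may already have been drawn, and wording cannot change those.

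These points limit the size of the problem. They do not remove the opening for infection, and they do not explain why blood has a 28-day window when tissue in the same comparison has 7.

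**Conclusion.** The point holds at a modest level. As written, the protocol allows a compliant baseline-to-Day 8 blood comparison in which 28 of 35 days are untreated, and it allows the baseline to be taken during a treated infection. The planned paired analysis cannot separate that recovery from a pembrolizumab effect.

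The window and day counts rest on the text alone. The false-positive rates rest on an assumed 1 SD shift and assumed fractions, and run from negligible (about 10%) to large (about 43%). A reader might take the upper values as expected error rates; the documents do not support that, because they give neither draw dates nor event rates. Nor do they support reading this as a threat to the trial's efficacy conclusions, since only exploratory PBMC and plasma markers are touched. Any effect on the correlations with PFS and OS has not been quantified. The matter is worth considering because the remedy is cheap, not because large harm has been shown.

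**What to change.** **Protocol text.** In Section 5.1 and Appendix D footnotes 18 and 19, require baseline PBMC and plasma pre-dose on Cycle 1 Day 1, with a fallback of within the 7 days before it. That is the window already used for the biopsy and safety laboratory tests. Leave the pharmacogenomic whole-blood sample at 28 days. The interval to Day 8 becomes 7 days, or at most 14 under the fallback.

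**Samples already drawn.** Report the draw-to-dose interval for each patient, and repeat the baseline-to-Day 8 analysis restricted to baselines taken within 7 days of dosing.

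**Consistency.** Reconcile the steroid-free intervals in Section 4.2 (exclusions 5 and 12) with the Screening-period prohibition in Section 6.5.2.

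**Cost.** The change is to wording. Every treated patient attends Cycle 1 Day 1 and the draw is already allowed then, so no visit or procedure is added. The downsides are an occasional missed Day 1 draw, which the fallback is there to cover, and fewer pairs in the restricted analysis.
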